3.3 Rationale for dose/regimen, route of administration and duration of treatment

QAW039 will be administered at doses of 150 mg once daily and 450 mg once daily as oral film-coated tablets (FCTs) in this study. The rationale supporting the inclusion of these 2 doses is below.

A 450 mg once daily dose was selected for inclusion in the study based on the following:

- At a dose of 450 mg once daily, >98% receptor occupancy is expected for the entire dosing interval in a “typical patient” at steady state allowing inhibition of eosinophil migration over the entire treatment interval.
- A 500 mg once daily dose of QAW039 was efficacious on the endpoint of predose FEV1 in a sub-set of patients with % predicted FEV1 <70% at Baseline in Study CQAW039A2201 proof-of-concept study (PoC).
- In study CQAW039A2206, a 450 mg total daily dose of QAW039 was also efficacious on the endpoint of predose FEV1.
- A total daily dose of 450 mg (225 mg twice daily) was evaluated in Study CQAW039A2208 in patients with severe asthma as add-on to SoC asthma therapy. In this study, QAW039 caused significant reduction of sputum eosinophilia in patients with severe eosinophilic asthma. The reduction in sputum eosinophils was comparable to that observed with the anti-IL5 antibodies, Mepolizumab (Pavord, et al 2012) and Reslizumab (Castro, et al 2011 and Castro, et al 2015). An association between reduction of eosinophilic airway inflammation and frequency of exacerbations has been reported in the literature (Haldar, et al 2009; Pavord, et al 2012; Nowak et al 2015; Wenzel, et al 2013; Takaku, et al 2013), suggesting QAW039 may also cause a reduction in the frequency of asthma exacerbations in patients with severe eosinophilic asthma.

[figure not shown]
The dose of 150 mg once daily was selected for inclusion in the study because it was the lowest dose of QAW039 with “maximal efficacy” on the endpoint of predose FEV1 in a prior dose-ranging study (Study CQAW039A2206) in patients with moderate-to-severe asthma (GINA treatment steps 4 and 5) as add-on to low-dose ICS. This dose is 0.5 log lower than highest dose.

Since the QAW039 dose of 150 mg was considered the optimal dose (i.e., lowest dose providing maximal efficacy) in a prior dose-ranging study, doses lower than 150 mg will not be included in this study.

The 2 doses of QAW039 included in this study are also being evaluated in other Phase 3 studies of QAW039 in patients of various asthma severities:

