7.2 Serious adverse events

7.2.1 Definition of SAE

An SAE is defined as any adverse event [appearance of (or worsening of any pre-existing)] undesirable sign(s), symptom(s) or medical condition(s)) which meets any one of the following criteria:

- is fatal or life-threatening
- results in persistent or significant disability/incapacity
- constitutes a congenital anomaly/birth defect
- requires inpatient hospitalization or prolongation of existing hospitalization, unless hospitalization is for:
 - routine treatment or monitoring of the studied indication, not associated with any deterioration in condition (specify what this includes)
 - elective or pre-planned treatment for a pre-existing condition that is unrelated to the indication under study and has not worsened since signing the informed consent
 - treatment on an emergency outpatient basis for an event not fulfilling any of the definitions of a SAE given above and not resulting in hospital admission
 - social reasons and respite care in the absence of any deterioration in the patient's general condition
- is medically significant, e.g. defined as an event that jeopardizes the patient or may require medical or surgical intervention.

All malignant neoplasms will be assessed as serious under “medically significant” if other seriousness criteria are not met.

Life-threatening in the context of a SAE refers to a reaction in which the patient was at risk of death at the time of the reaction; it does not refer to a reaction that hypothetically might have caused death if it were more severe (see Annex IV, ICH-E2D Guideline).

Medical and scientific judgment should be exercised in deciding whether other situations should be considered serious reactions, such as important medical events that might not be immediately life threatening or result in death or hospitalization but might jeopardize the patient or might require intervention to prevent one of the other outcomes listed above. Examples of such events are intensive treatment in an emergency room or at home for allergic bronchospasm, blood dyscrasias or convulsions that do not result in hospitalization or development of dependency or abuse (see Annex IV, ICH-E2D Guideline).

Any suspected transmission via a medicinal product of an infectious agent is also considered a serious adverse reaction.

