9.4.1 Variables

The primary variables for the study are:

- Time-to-first treatment emergent AE;
- Time-to-first treatment emergent SAE; and
- Time-to-first treatment emergent AE leading to discontinuation from study treatment.

Adverse events (including asthma exacerbations), starting on or after the time of the first intake of study drug and until the day after the last intake of study drug will be classified as treatment emergent AEs. Any AEs that started during the study after informed consent and before the time of the first intake of study drug will be classified as a prior AE and not classified as treatment emergent AE. The time-to-first treatment emergent AE will be defined as the time to the occurrence of an AE from the treatment start date, and will be computed as time to AE=AE start date-treatment start date+1 day. Treatment emergent SAEs and AEs leading to discontinuation from study treatment will be defined in a similar manner.

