While no formal hypothesis testing is foreseen for the primary safety objectives, if both QAW039 doses have a 50% relative hazard increase for treatment emergent events, compared with placebo, then there will be approximately > 99%, 94% and 38% power that the two-sided 95% confidence interval not adjusted for multiplicity for one of the two QAW039 doses would exclude no effect for the primary safety variables of time-to-first treatment emergent AE, time-to-first treatment emergent SAE, and time-to-first treatment emergent AE leading to study treatment discontinuation analyzed across Treatment Period 1 and Treatment 2 combined, respectively. The power was estimated using 10,000 simulations based on 1,570 patients being randomized into the current study. In addition, the sensitivity of the power is further assessed for different scenarios of sample size (1470 patients and 1670 patients). This power will be higher, if more patients are randomized (e.g., due to additional new patients being enrolled) or more patients completing prior Phase 3 studies of QAW039 elect to participate in the current study.

The underlying assumptions for the power simulations were an exponential censoring rate in the placebo group of 0.22 and of 0.16 in the QAW039 treatment groups. The assumptions on the exponential event rate in each treatment group are shown in [Table 9-1](#). These assumptions are based on the, DREAM ([Pavord et al. 2012](#)) and MENSA ([Ortega et al. 2014](#)) trials, as well as a QAW039 Phase 2 study in moderate-to-severe asthma. The detailed power calculations are shown in the [Table 9-2](#) and [Table 9-3](#).

Table 9-1 Assumed placebo event rates for power calculations

Endpoint	Previous study patients were enrolled in or new patients	Assumed exponential event rate (per patient-year)
Rate of AEs	QAW039A2316/ QAW039A2317	3.01
	QAW039A2307/ QAW039A2314	2.86
	New patients	2.86
Rate of SAEs	QAW039A2316/ QAW039A2317	0.07
	QAW039A2307/ QAW039A2314	0.24
	New patients	0.24
Rate of AEs leading to study treatment discontinuation	QAW039A2316/ QAW039A2317	0.03
	QAW039A2307/ QAW039A2314	0.03
	New patients	0.03

Table 9-2 Power (%) for a non-multiplicity adjusted confidence interval to exclude no-difference versus placebo for the primary safety variables

Primary Endpoint	Treatment Period	QAW039 150 mg versus placebo	QAW39 450 mg versus placebo	Both QAW039 150 mg and 450 mg versus placebo	One of the two QAW039 doses versus placebo
Time-to-first AE	1	>99	>99	>99	>99

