2.5 Analysis of the primary objective

2.5.1 Primary endpoint

Primary endpoints for the study are:

Treatment Period 1:

- Time-to-first treatment emergent adverse events (AEs);
- Time-to-first treatment emergent serious adverse events (SAEs); and
- Time-to-first treatment emergent AE leading to discontinuation from study treatment.

of QAW039 (150 mg once daily and 450 mg once daily), compared with placebo in patients with moderate-to-severe asthma receiving SoC asthma therapy.

Treatment Period 1 and Treatment Period 2 combined:

- Time-to-first treatment emergent adverse events (AEs);
- Time-to-first treatment emergent serious adverse events (SAEs); and
- Time-to-first treatment emergent AE leading to discontinuation from study treatment.

of QAW039 (150 mg once daily and 450 mg once daily), compared with placebo in patients with moderate-to-severe asthma receiving SoC asthma therapy.

As this study has been early terminated, the primary endpoint will be analyzed in the way of combined treatment period 1 and treatment period 2. Treatment emergent AEs are defined as adverse events (including asthma exacerbations), starting on or after the day of the first intake of study drug in this study and until the earlier date out of: date of last intake of study drug +7 days (30 days in the case of a serious AE) and final visit.

Any AEs that started during the study after informed consent and before the time of the first intake of study drug will be classified as a prior AE and not classified as treatment emergent AE. The time-to-first treatment emergent AE is defined as the time to the occurrence of an AE from the treatment start date, and computed as time to AE=AE start date – treatment start date +1 day. As a general rule of censoring, patients who either completed the study or discontinued

treatment prematurely or continued treatment and without the event of interest will be censored at the minimum out of the dates of last medication intake + 30 days, final visit date, and date of death. Time-to-first treatment emergent SAEs and time-to-first treatment emergent AEs leading to discontinuation from study treatment are defined in a similar manner as time-to-first treatment emergent AE.

The definition and rationale for the estimand for the primary endpoint are given in [Table 2-1](#). The statistical strategy to handle each intercurrent event is described in more detail in [Section 2.5.3](#).

Table 2-1 Summary of estimand for the primary endpoint

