Population		Justification	

Male or female patients aged 12 years and older with moderate-to-severe asthma on standard-of-care asthma therapy and receive at least one dose of study treatment, including two categories of patients:
 
 • Rollover patients: patients completing a prior Phase 3 study (A2307, A2314, A2316, or A2317) of fevipirant; and • New patients: patients with inadequately controlled asthma who had not previously participated in a study of fevipirant. 		
Fevipirant (QAW039) is a Prostaglandin D2 receptor 2 (DP2) antagonist expected to provide benefit in asthma by impacting major effector cells and soluble factors driving airway inflammation in asthma. Treatment with fevipirant should result in a decrease in these parameters of airway inflammation as well as a clinical improvement in asthma.
	
Variables		Justification	

 • Time-to-first treatment emergent AEs • Time-to-first treatment emergent SAEs and • Time-to-first treatment emergent AE leading to discontinuation from study treatment. 		
The primary endpoints provide safety assessments with respect to the timing of first occurrence of treatment emergent AEs, SAEs, and AEs leading to study treatment discontinuation.
	
Intercurrent event	Description	Strategy to handle event	Justification
Discontinuation of fevipirant for any reason without experiencing a safety outcome as defined in the primary variables	Discontinuation of fevipirant for any reason regardless of relation to fevipirant without experiencing a safety outcome as defined in the primary variables	A hypothetical strategy will be used assuming a continued risk for a first event after study treatment discontinuation as described in Section 2.5.3	
These patients may discontinue therapy in clinical practice. Any fevipirant treatment effect would cease almost instantly after discontinuation of fevipirant, and only SoC effect is expected.
 
The safety outcomes would be no more or less likely to occur after discontinuation of fevipirant.

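### The primary AE and SAE hazard ratios count asthma exacerbations, which the drug may reduce, so they can dilute a real excess of other events; report an exacerbation-free analysis beside them

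*SAP*

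**What the plan says.** Both documents put exacerbations in the primary event definition. Protocol 9.4.1 reads "Adverse events (including asthma exacerbations), starting on or after the time of the first intake of study drug", and SAP 2.5.1 begins "Treatment emergent AEs are defined as adverse events (including asthma exacerbations". The SAP adds that the times to first SAE and to first AE leading to discontinuation "are defined in a similar manner as time-to-first treatment emergent AE". Under Protocol 7.2.1 an event is serious if it "requires inpatient hospitalization or prolongation of existing hospitalization, unless hospitalization is for" one of the listed exceptions. The exception for the studied indication covers only routine care without deterioration, so an exacerbation that leads to admission is an SAE.

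The same documents anticipate benefit in asthma. Protocol 3.3 describes a fall in sputum eosinophils as "suggesting QAW039 may also cause a reduction in the frequency of asthma exacerbations in patients with severe eosinophilic asthma". The estimand table in SAP 2.5.1 calls the drug "expected to provide benefit in asthma by impacting major effector cells and soluble factors driving airway inflammation in asthma".

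The power case in Protocol 9.8, repeated in SAP section 3, asks what happens "if both QAW039 doses have a 50% relative hazard increase for treatment emergent events, compared with placebo". It judges this by whether a "two-sided 95% confidence interval not adjusted for multiplicity" excludes no effect. That increase applies to every treatment-emergent event, exacerbations included.

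**The concern.** The sole purpose of the study is safety, and its headline results are hazard ratios for first AE and first SAE. If one component of those endpoints may fall on active drug while another rises, the combined ratio is a weighted average of the two. A value near 1 could then mean no harm, or harm offset by benefit, and the primary analysis cannot tell these apart.

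Counting only the first event adds a second effect. A patient with an early serious exacerbation leaves the risk set, so a later non-asthma SAE in that patient never enters the model. Nor does the stated SAE power describe the case of most interest, which is harm confined to non-asthma events.

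**Working it through.** **Inputs from Protocol 9.8, 3.2 and 5.3.** There are 1,570 patients (1,000 rollover, 570 new), with placebo 1/7 and each dose about 3/7. Placebo SAE rates are 0.07 per patient-year (A2316/A2317) and 0.24 (A2307/A2314 and new patients). Censoring rates are 0.22 on placebo and 0.16 on active. Follow-up T is 1 year for Period 1 and 3 years for both periods.

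**Inputs not in the documents (assumptions).**
- The rollover split. Single-dose 3-year SAE power runs from 75% to 93% as the number from A2307/A2314 goes from 0 to 1,000. A value of 650 to 750 matches the plan. I show 700 and 800.
- The share s of the placebo SAE hazard that is exacerbations, taken as equal across strata.
- The hazard ratio for exacerbations.

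**Formulas.** Expected first events per arm and stratum are n × L/(L+c) × (1 − exp(−(L+c)T)), where L is the event rate and c the censoring rate. Single-dose power is Φ(ln HR / √(1/d0 + 1/d1) − 1.96), where d0 and d1 are placebo and active events. Power for both doses uses a bivariate normal whose correlation, (1/d0)/(1/d0 + 1/d1), comes from the shared placebo arm. Power for at least one dose is twice the single-dose power minus the power for both. Only intervals that exclude 1 upward are counted.

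**Step 1: reproduce the plan.** With 700 from A2307/A2314, T = 3 and HR 1.5, d0 = 76.9 and d1 = 325.6. Then 0.405/√(1/76.9 + 1/325.6) − 1.96 = 1.24, which gives 89.2% per dose. Both doses give 84.7%, and at least one gives 2 × 89.2 − 84.7 = 93.7%. The plan states 89, 84 and 94. With 800, at least one dose gives 94.6%. A stratified Cox simulation at 700 (1,500 runs, six strata with their own ratios) gave 90.6% and 89.1% for the two doses, 84.2% for both and 95.5% for at least one. For Period 1 the closed form gives 61% per dose and the simulation about 63%, against 65% stated.

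**Step 2: composite hazard ratio.** With constant hazards, HR = s × HR_exac + (1 − s) × 1.5. At HR_exac = 0.7:
- s = 0.10: 0.07 + 1.35 = 1.42
- s = 0.30: 0.21 + 1.05 = 1.26
- s = 0.45: 0.315 + 0.825 = 1.14
- s = 0.60: 0.42 + 0.60 = 1.02

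**Step 3: power for at least one dose, 156 weeks.** The exacerbation-free endpoint uses placebo rates multiplied by (1 − s) and HR 1.5. Ranges cover 700 to 800 rollovers from A2307/A2314.

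| Asthma share s | Composite HR | Composite power | Exacerbation-free power |
|---|---|---|---|
| 10% | 1.42 | 86-87% | 92-93% |
| 30% | 1.26 | 54-56% | 87-88% |
| 45% | 1.14 | 24-25% | 80-82% |
| 60% | 1.02 | 6% | 69-71% |

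Worked row, s = 0.30 with 700. The composite has d0 = 76.9 and d1 = 291.0, so 0.231/√(1/76.9 + 1/291.0) − 1.96 = −0.16. That is 43.7% per dose, 33.4% for both and 54% for at least one. The exacerbation-free endpoint has d0 = 58.4 and d1 = 256.6, giving 79.8%, 73.0% and 87%.

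**Step 4: no effect on exacerbations.** With HR_exac = 1.0 and s = 0.30 the composite HR is 1.35. Power is 75-77%, against 87-88% without exacerbations. Dilution therefore needs no benefit at all.

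**Step 5: exact cancellation.** Composite HR = 1 requires s = 0.5/(1.5 − HR_exac): 50% at HR_exac 0.5, 62.5% at 0.7 and 71% at 0.8.

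**Step 6: the AE endpoint.** One dose against placebo, 156 weeks, 700 from A2307/A2314. At HR_exac 0.7, composite power is 99% at s = 0.10, 83% at 0.30 and 22% at 0.50. The exacerbation-free AE endpoint stays above 99% throughout.

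**The case against.** **The premises are softer than they look.** A reader might infer that the protocol firmly expects fewer exacerbations and that these are a main source of SAEs here. The documents support neither. Protocol 3.3 says only that the drug *may* reduce them, and only in severe eosinophilic asthma. New patients need no eosinophil threshold, and A2316/A2317 patients are at GINA steps 3 and 4. Investigators may adjust background therapy (Protocol 5.5.7), which could shrink any difference. No asthma share of AEs or SAEs is given. This stands, and it is why the sizes above are illustrations.

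**The report shows more than one number.** SAP 2.8.1 plans a logistic model of AEs for each system organ class, with odds ratios and intervals. A patient with an exacerbation and a later event in another class counts in both. SAEs are tabulated by class and preferred term with exposure-adjusted rates. Serious AEs of special interest, exacerbation hospitalisations and asthma deaths are summarised separately, and the DMC sees unblinded data. So a harm would be obscured in the primary hazard ratio, not in the whole report. This also stands. But the logistic models cover AEs rather than SAEs, one class at a time, and patient counts cannot be summed across table rows because one patient may appear in several. No visible analysis gives a hazard ratio for non-asthma SAEs.

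**The composite is legitimate.** Asthma worsening is itself a safety outcome, the definition is consistent on this point across both documents, and no formal hypothesis test is planned. This is a reason to keep the composite as primary, not a reason to leave it on its own.

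**Redaction.** Protocol 9.4.4 and several SAP sections are not visible, so a related analysis cannot be ruled out. SAP section 4 does say that the 9.4.4 supportive analyses will apply to incidence-rate summaries rather than the primary outcome.

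**Conclusion.** The point holds as one of dilution. The primary AE and SAE hazard ratios combine exacerbations with all other events, and on their own they cannot separate absence of harm from harm partly offset by benefit. With HR 1.5 for other SAEs and 0.7 for exacerbations, power to detect the excess falls modestly at a 10% asthma share and severely from 30% upward.

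The stronger reading, that the expected benefit will cancel a real excess, is not supported. At an exacerbation ratio of 0.7 it needs an asthma share of about 62%, and the documents give no share. Nor does removing exacerbations restore the stated 94%, because events are lost: the exacerbation-free endpoint reaches 69% to 93% over the shares shown.

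All of this rests on the assumed share, exacerbation ratio and rollover split, on constant hazards, and on a 156-week horizon. SAP 2.5.1 says the study was terminated early, so actual power is likely to be lower for both endpoints. The addition is worth making because it is cheap and changes what the trial can conclude.

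**What to change.** Keep the composite primary unchanged. Add to SAP 2.5.2, as supplementary analyses, the same stratified Cox model for time to first AE and time to first SAE excluding asthma exacerbations. Specify three things:
- Exacerbations are identified by a preferred-term list fixed in advance, together with the exacerbation eCRF records.
- Follow-up continues past an exacerbation, so that a later non-asthma event counts.
- The hazard ratios and 95% intervals are reported beside the primary result.

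This takes two more model runs on data already collected. The downside is wider intervals from fewer events. With 700 rollovers from A2307/A2314, expected placebo first SAEs over 156 weeks fall from 76.9 to 58.4 at a 30% share and to 36.3 at 60%. At 30%, the standard error of the log hazard ratio rises from √(1/76.9 + 1/291.0) = 0.128 to √(1/58.4 + 1/256.6) = 0.145, about 13% wider.
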